**Figure 1. MiniMed™ 670G Insulin Pump**

### 7.3.2. **Guardian™ Sensor (3)**

The Guardian™ Sensor (3) is a glucose sensor that contains one microelectrode with a thin coating of glucose oxidase beneath several layers of biocompatible membrane. The sensor is the latest generation of glucose sensors with design changes supporting improved accuracy. It is intended to penetrate the skin at a 90-degree angle. The sensor is tubeless and as a result has a smaller volume than previous Medtronic MiniMed sensors. An introducer needle penetrates the skin surface and provides support for the sensor microelectrode during insertion. The sensor continuously converts small amounts of glucose from the subject's interstitial fluid into an electronic signal that is received by a transmitter or recorder, the strength of which is proportional to the amount of glucose present in the blood. The electrode is composed of embedding, signal-conducting and insulating layers.

**Figure 2. Guardian™ Sensor (3)**

### 7.3.3. **Guardian™ Link (3) Transmitter**

The Guardian™ Link (3) transmitter is a device that reads the electronic signal generated by the sensor. In addition, the transmitter contains a custom Application Specific Integrated Circuit (ASIC), which enables Electrochemical Impedance Spectroscopy (EIS). The EIS measurements are used as diagnostics for the sensor, which are incorporated into the sensor calibration logic.

In addition, the transmitter also contains the sensor calibration algorithm which converts the sensor signal to a SG value using calibration BG values from a meter relayed to the transmitter through the pump. The algorithm is designed to improve and optimize performance when paired with the sensors.

In this study the Guardian™ Link (3) transmitter will be connected to a Guardian™ Sensor (3).

**Figure 3. Guardian Link (3) Transmitter**

### 7.3.4. **One-press Serter**

The One-press Serter, referred to as the Serter (Figure 3) in this protocol, is an insertion device that is used to ensure correct placement of the Guardian™ Sensor (3) into the user's subcutaneous tissue. Insertion is triggered when the two spring loaded buttons on the sides of the Serter are pressed simultaneously. The Serter is intended as a single patient, non-sterile, multi-use device.

**Figure 4. One-press Serter**

### 7.3.5. Charger

The Charger is used to recharge the Guardian™ Link (3) Transmitter as needed. The charger operates using disposable batteries and will recharge the Guardian™ Link (3) Transmitter according to the user guide.

**Figure 5. Charger**

### 7.3.6. Tester

The Tester operates as a sensor simulator creating signal current at a level that is within the range of an in-vivo sensor during normal operation. It is used to test and clean the Guardian™ Link (3) Transmitter.

**Figure 6. Tester**

### **7.3.7. Roche Accu-Chek™\* Guide Link Meter**

The Accu-Chek™\* Guide Link Meter Blood Glucose Monitoring System is comprised of the Accu-Chek™\* Guide Link Meter and Accu-Chek™\* Guide Link test strips. This Blood Glucose Monitoring System is intended to quantitatively measure glucose in fresh capillary whole blood from the fingertip, palm, and upper arm as an aid in monitoring the effectiveness of glucose control. The Accu-Chek™\* Guide Blood Glucose Monitoring System is intended for in vitro diagnostic single-patient use by people with diabetes. Transmission of data is via Bluetooth® Low Energy.

### **7.3.8. Blue adapter**

The Blue Adapter is a USB accessory that allows for data uploads from the MiniMed™ 670G insulin pump to CareLink™ For Clinical Research via USB interface of the PC or Mac devices.

### **7.3.9. Mobile Application**

The MiniMed Mobile Application, referred to as Mobile App in the protocol, is an optional accessory to the MiniMed™ 670G insulin pump and provides a secondary display and passive monitoring of pump data for users with compatible electronic devices. The Mobile App is available for both iOS and Android platforms.

## **7.4. Non-Investigational Devices**

The non-investigational device used in the study will be described in this section. Instructions for intended use, including indications, contraindications, and precautions of the components used in this study, are provided in their respective user guides/instructions for use (IFU).

### **7.4.1. CareLink™ For Clinical Research Software**

Medtronic CareLink™ For Clinical Research is an web-based system which allows the device data to be viewed and easily evaluated by the subject and his/her physician. A PC links to the Medtronic CareLink™ system via the Internet, which then allows subjects and investigational center staff to upload data from Medtronic MiniMed insulin pumps and third-party BG meters. The clinical support version of Medtronic CareLink™ For Clinical Research will be used by the investigational center staff and subjects. All references to CareLink™ For Clinical Research software are meant to imply the clinical support version of Medtronic

CareLink™ and throughout the protocol will be referred to as CareLink™ software. The data contained in CareLink™ For Clinical Research software is accessible to users using a standard browser, i.e., Microsoft® Internet Explorer, on an Internet enabled PC.

The CareLink™ software system uses standard Transport Layer Security (TLS) technology. The TLS transmission protocol invokes encryption on both ends of the transmissions and is the standard for all security-based systems. The encryption remains in effect whether the data is moving to and from the client and server in the United States, or to and from a client in another country to the United States. The data is secure behind a three-tier industry standard architecture, which places the database behind three different firewalls, where each firewall separates a tier:

- The internet to the web server;
- Web server to the application server;
- Application server to the database server.

#### **7.4.2. Abbott™\* FreeStyle Optium Neo Blood Glucose & Ketone Monitoring System**

The Abbott™\* FreeStyle Optium Neo Blood Glucose & Ketone Monitoring System, referred to as FreeStyle Optium Neo ketone meter throughout this protocol, measures both blood glucose (sugar) and blood  $\beta$ -Ketone. In this study, the meter will be used to collect  $\beta$ -Ketone data, which will be collected for reporting and review (see Investigator Site binder for details) and as described in the body of this study protocol. This particular meter will be used because it is the only commercially available meter which allows quantification of blood  $\beta$ -Ketone levels and is the preferred patient method of testing over urine testing.

Note: In the event the blood ketone meter is not used to collect ketone values, urine ketones must be measured and entered into CareLink™ software instead.

#### **7.5. Consumable devices**

Infusion sets, reservoirs, infusion set seter devices, glucose meter accessories and other consumable materials will be provided to subjects for use in the study.

#### **7.6. Insulin**

Subjects will use the rapid-acting analogue insulin (Novolog™\* or Humalog™\*) during this study.

#### **7.7. Smartphone**

Subjects will use their own Smartphone during this study.

## 7.8. Device Accountability

Good clinical research practice requires that investigators and research teams ensure accurate accountability for any investigational device used in a research trial. It is expected that all investigational devices will be used in the manner intended during the study, that they will be stored under appropriately controlled conditions and that they will be used only by (on) subjects who have consented to participate in the research study.

Any investigational device being used in clinical research must be strictly accounted for and will not be shipped to any site unless all of the necessary approvals (e.g. Regulatory, EC) have been received. This includes keeping records of:

1. Center receipt and inventory management
2. Storage
3. Subject Disbursement
4. Return (by subjects and investigational center) and/or disposal

The labeling of commercial devices will be provided in accordance with local language requirements.

In China, all study devices will be labeled as per local regulations in China. Investigational devices will be labeled "Clinical trial use only" in accordance with NMPA Order No. 25.

During the conduct of the study the investigational center staff will account for, and document, the following:

**Table 2 Device Accountability Requirements**

Device	Record on Site Received eCRF	Record Disbursement, Returned or Not Returned from Subject on Device Identification eCRF	Subject Return Device to Investigational Center	Record Returned or Not Returned on Site Returned eCRF	Site Return Device to Sponsor at Conclusion of Study
MiniMed™ 670G Insulin Pump (MMT-1883)	Yes	Yes	Yes	Yes	Yes
Guardian™ Sensor (3) (MMT-7020)	Yes	Yes	Yes (Unused only)	Yes (Unused only)	Yes (Unused only)
Kit (MMT-7910)	Guardian™ Link (3) Transmitter* (MMT-7911)	Yes	Yes	Yes	Yes
	One-press Serter (MMT-7512)*	Yes	Yes	Yes	Yes
	Charger (MMT-7715)*	Yes	Yes	Yes	Yes

---

*Medtronic Confidential*

# CIP329 Clinical Investigation Plan

10939060DOC

Version C

Page 39 of 99

Medtronic

	Tester (MMT-7736L)*	Yes	Yes	Yes	Yes	Yes
Accu-Chek™* Guide Link study meter (Model MTR114)		Yes	Yes	Yes	Yes	Yes
Blue adapter (ACC-1003910)		Yes	Yes	Yes	Yes	Yes
FreeStyle Optium Neo Ketone Meter		No	No	No	No	Yes (Unused only)

\*Devices may be combined and distributed in kits.

---

*Medtronic Confidential*

The investigational center will promptly notify the sponsor of any device handling violation that might impact either the safety and/or welfare of subjects or data integrity.

### **7.8.1. Receipt and Inventory of Investigational Devices by Investigational Center**

- Upon receipt of the study devices, investigational center staff take inventory of the shipment, making sure that information on the packing slips/invoices matches exactly the contents of the containers, as applicable, including:
  - Ship to Address
  - Reference Number
  - Device Type
  - Quantity
  - Quantity per package
  - Lot number (where applicable)
  - Serial number (where applicable)
- Ensure that devices and supplies received have not reached or exceeded their expiration date
- Sign and date the packing slips/invoices, noting any discrepancies, and file in appropriate study binder
- Notify the study monitor of any discrepancies
- Enter the study device information on the appropriate eCRFs in the study database, if applicable.

### **7.8.2. Storage of Study Devices at Investigational Center**

Study devices are to be stored in a secure environment with access limited to authorized research personnel. Study devices are stored in the proper environmental conditions, as identified in the IFU/labeling.

### **7.8.3. Disbursement of Study Devices**

Each time a study device is disbursed to a subject by the investigator or authorized member of the research team, all required eCRF and source documentation will be completed. Documentation may include:

- Date of disbursement
- Subject ID
- Lot number(s)

---

*Medtronic Confidential*

- Serial Number
- Reference Number
- Amount dispensed

## 7.8.4. Return or Disposal of Study Devices

After use by the subject, the investigational center is expected to accept and retain all devices as described in Table 2 and store them in a secure environment. If containers/units/devices are missing, the reasons should be documented in the applicable eCRF. If discrepancies between the amounts used by subjects and the amounts expected to be returned exist, the reasons should be documented in the applicable eCRF.

Requirements for return of devices by subjects to the investigational center and return of device by the investigational center to the sponsor are listed in Table 2. The devices that are being returned to the investigational center may be returned to the sponsor as subjects complete the study, at the EOS visit or upon sponsor request.

Other unused consumable devices (i.e., infusion sets, alcohol wipes, study meter supplies, tape, etc.), supplies or materials may be returned to the sponsor, they may be retained by investigational centers for educational purposes only, or they may be disposed of properly by the investigational center staff.

Disposable devices and supplies that have been *used* by a subject will be disposed of properly by the subject or the investigational center staff during the conduct of the study.

All study devices that are required to be entered into the study database must be accounted for as described above before they are returned to the sponsor.

## 8. Selection of Subjects

### 8.1. Study Population

This study will enroll subjects between age of 14 and 75 years old, with a ratio (1:5) between Adolescents (14-17 years) and Adults ( $\geq 18$  years).

A total of up to 75 subjects will be enrolled at minimum 2 investigational centers and up to 6 investigational centers (hospitals) in China considering potential drop outs. A maximum of 30 subjects will be enrolled at each investigational center. Sites with less than 6 subjects will be pooled into 'pseudo-sites' of at least 10 subjects per pseudo-site. Pseudo-sites will be pooled by ranking those sites with less than 6 subjects by site number and pooling those sites in order of site number until the number of subjects reaches at least 10.

### 8.2. Subject Enrollment

Subjects will be considered enrolled in the study upon signing the Informed Consent Form (ICF) and

*Medtronic Confidential*

assent form (if applicable).

A subject will be assigned a unique study subject identification (ID) via the eCRF, which is a 9-digit code (329XXXXXX). The first three numbers refer to the CIP number (329), the next three numbers refer to the investigational center number, and the last 3 numbers refer to the subject number assigned during Visit 1 (e.g., 329002001 is subject 001 from site 002).

The investigator will maintain a log of all subjects enrolled in the clinical study, assigning a subject ID linked to their names, alternative subject ID, and contact information.

### **8.3. Inclusion Criteria**

#### *General Inclusion Criteria*

1. Subject is age 14- 75 years at time of Screening.
2. Subject has a clinical diagnosis of type 1 diabetes for 2 years or more as determined via medical record or source documentation by an individual qualified to make a medical diagnosis.

#### *Study-specific inclusion criteria*

3. Subject is willing to perform  $\geq$  4 finger stick BG measurements daily.
4. Subject is willing to perform required sensor calibrations.
5. Subject is willing to wear the system continuously throughout the study.
6. Subject must have a minimum daily insulin requirement (Total Daily Dose) of greater than or equal to 8 units.
7. Subject has a Glycosylated hemoglobin (HbA1c) less than 10% (as processed by the investigational center lab or their contracted Local Lab) at time of Screening visit.
8. Subject has thyroid-stimulating hormone (TSH) in the normal range OR if the TSH is out of normal reference range the Free T3 is below or within the lab's reference range and Free T4 is within the normal reference range. Prior labs in the last 6 months are sufficient.
9. Subject has been on pump therapy for greater than 6 months prior to screening (with or without CGM experience).
10. Subject is willing to upload data from the study pump and meter at home.
11. If subject has celiac disease, it has been adequately treated as determined by the investigator.
12. Subject has been taking and is willing to take one of the following insulins throughout the course of the study:
  - o Humalog™\* (insulin lispro injection)
  - o NovoLog™\* (insulin aspart)
13. Subject must be able to carbohydrate count or willing to learn how to carbohydrate count for the study.

### **8.4. Exclusion Criteria**

1. Subject has a history of 2 or more episodes of severe hypoglycemia, which resulted in any the following during the 6 months prior to Screening:

*Medtronic Confidential*

- a. Medical assistance (i.e. Paramedics, Emergency Room (ER) or Hospitalization)
  - b. Coma
  - c. Seizures
2. Subject has been hospitalized or has visited the ER in the 6 months prior to Screening resulting in a **primary diagnosis** of uncontrolled diabetes.
3. Subject has had DKA in the 6 months prior to Screening.
4. Subject is unable to tolerate tape adhesive in the area of sensor placement.
5. Subject has any unresolved adverse skin condition in the area of sensor placement (e.g., psoriasis, dermatitis herpetiformis, rash, Staphylococcus infection).
6. Subject is a female of child-bearing potential who has a positive pregnancy test at Screening or plans to become pregnant during the course of the study.
7. Subject is a female who is sexually active and able to conceive should be excluded if they are not using an effective method of contraception and do not agree to continue using an effective method of contraception for the duration of the study as determined by investigator.
8. Subject has had any of the following cardiovascular events within 1 year of screening: myocardial infarction, unstable angina, coronary artery bypass surgery, coronary artery stenting, transient ischemic attack, cerebrovascular accident, angina, congestive heart failure, ventricular rhythm disturbances or thromboembolic disease.
9. Subject is being treated for hyperthyroidism at time of Screening.
10. Subject has a diagnosis of adrenal insufficiency.
11. Subject has taken any oral, injectable, or intravenous (IV) glucocorticoids within 8 weeks from time of Screening, or plans to take any oral, injectable, or IV glucocorticoids during the course of the study.
12. Subject is actively participating in an investigational study (drug or device) wherein he/she has received treatment from an investigational study drug or investigational study device in the last 2 weeks. (Please note participation in an observational study is acceptable.)
13. Subject is currently abusing illicit drugs.
14. Subject is currently abusing alcohol.
15. Subject is using pramlintide (Symlin), DPP-4 inhibitor, liraglutide (Victoza or other GLP-1 agonists), metformin, canagliflozin (Invokana or other SGLT2 inhibitors) at time of Screening.
16. Subject has a history of visual impairment which would not allow subject to participate in the study and perform all study procedures safely, as determined by the investigator.
17. Subject has elective surgery planned that requires general anesthesia during the course of the study.
18. Subject has a sickle cell disease, hemoglobinopathy; or has received red blood cell transfusion or erythropoietin within 3 months prior to time of Screening
19. Subject plans to receive red blood cell transfusion or erythropoietin over the course of study participation.
20. Subject diagnosed with current eating disorder such as anorexia or bulimia
21. Subject has been diagnosed with chronic kidney disease that results in chronic anemia.
22. Subject has a hematocrit (Hct) that is below the normal reference range of lab used. Prior labs in the last 6 months are sufficient.
23. Subject is on dialysis.
24. Subject has an estimated glomerular filtration rate (eGFR) of < 30.
25. Subject has a pediatric BMI category of underweight (less than the 5th percentile) as defined by Centers for Disease Control (CDC)  
([https://www.cdc.gov/healthyweight/assessing/bmi/childrens\\_bmi/about\\_childrens\\_bmi.html](https://www.cdc.gov/healthyweight/assessing/bmi/childrens_bmi/about_childrens_bmi.html))
26. Subject is a member the research staff involved with the study.

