## 9.10. Subject Withdrawal or Discontinuation

Subjects may choose to withdraw from the study at any time by notifying investigational center staff of their intent.

If a subject chooses to end his or her study participation or if the subject is removed from the study at the investigator's discretion or for failure to meet the study requirements, the reason for withdrawal must be documented. All study devices and supplies must be returned (as applicable) and documented both in source documents and on an eCRF.

Subjects may also be withdrawn from the study at the discretion of the investigator. A subject may be withdrawn from the study if:

- In the opinion of the investigator, the subject's health or safety would be compromised by continuing in the study
- In the opinion of the investigator, it is in the subject's best interest to discontinue participation in the study
- The subject is found to no longer meet all inclusion criteria, or is found to meet one or more exclusion criteria
- The subject fails to comply with one or more study requirements
- The subject is lost to follow up
- During the course of the study, subject begins participation in another investigational study (drug or device).
- During the course of the study, subject begins abusing illicit drugs.
- During the course of the study, subject begins abusing alcohol.

- During the course of the study, subject begins using pramlintide (Symlin), DPP-4 inhibitors, liraglutide (Victoza or other GLP-1 agonists), metformin, canagliflozin (Invokana or other SGLT2 inhibitors).
- During the course of the study, subject receives red blood cell transfusion or erythropoietin.
- During the course of the study, the subject demonstrates that he/she is not able to comprehend instructions for study procedures, as evaluated by the appropriate research staff.
- During the course of the study, subject is taking oral, injectable, or IV glucocorticoids
- During the study, (female) subject becomes pregnant.
- During the study, the subject experiences one severe hypoglycemic episode
- During the study, the subject experiences one episode of DKA
- During the study, subject has a cardiovascular event or any vascular event such as stroke.

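### Exclusion 7 joins its two contraception conditions with *and*, so a woman using contraception at Screening who will not agree to continue it is not excluded by that item

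*Protocol*

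**What the plan says.** Protocol Section 8.4, item 7, is addressed to one group: "Subject is a female who is sexually active and able to conceive should be excluded". The condition follows: "if they are not using an effective method of contraception and do not agree to continue using an effective method of contraception", and the item closes with "for the duration of the study as determined by investigator". The synopsis repeats item 7 in the same words, so neither place corrects the other.

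Three other provisions bear on pregnancy:

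- Exclusion 6, in the same list, excludes a woman of child-bearing potential who "has a positive pregnancy test at Screening or plans to become pregnant during the course of the study".
- Section 9.10 lists, among reasons for which a subject may be withdrawn, "During the study, (female) subject becomes pregnant".
- Section 9.10 also lists "The subject is found to no longer meet all inclusion criteria, or is found to meet one or more exclusion criteria".

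The inclusion criteria in Section 8.3 contain no contraception requirement. Table 3 in Section 9.2 schedules the pregnancy test at Visit 1 only.

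**The concern.** Item 7 refers to the whole duration of the study, so it is evidently meant to secure protection beyond Screening. Read as a logical rule, it does not do that for the women to whom the commitment matters most, namely those who use contraception now and are asked to keep using it.

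Participation lasts roughly two to three months and the pregnancy test is scheduled once, at Visit 1. After Screening, item 7 is therefore the only preventive control in the plan that concerns contraception.

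Eligibility wording also has consequences elsewhere. Section 9.9.2 treats continued participation of a subject who does not meet all criteria as a significant deviation needing immediate notification of the sponsor. SAP Section 7.1.3 gives an eligibility violation as its example of a major deviation that removes a subject from the per-protocol set. With the present wording two sites could classify the same woman differently, and a monitor could not rely on the text to object to her enrolment.

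**Working it through.** No figure is involved, so the check is a truth table on the stated rule, followed by a comparison with the neighbouring provisions.

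**Inputs (Section 8.4, item 7).** Let A = not using effective contraception, and B = does not agree to continue using it. The item excludes when A and B both hold. Equivalently, item 7 does not exclude a woman who is using contraception or who agrees to continue.

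| Case | At Screening | Agrees to continue? | A | B | Excluded by item 7 as written? |
|---|---|---|---|---|---|
| 1 | Using | Yes | false | false | No |
| 2 | Using | No | false | true | **No** |
| 3 | Not using | Yes | true | false | No, read literally |
| 4 | Not using | No | true | true | Yes |

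Read literally, one of the four combinations is excluded.

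**How firm each case is.** Case 3 is open to argument, because continuing presupposes current use. On that reading a woman who is not using contraception cannot agree to continue, so B is true for every non-user and case 3 collapses into case 4. Item 7 then reduces to A alone, and its second condition excludes nobody whom the first does not already exclude. Case 2 comes out the same on both readings: A is false, so she is not excluded. The gap therefore does not depend on how case 3 is resolved.

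**Whether another provision catches case 2.**

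- *Exclusion 6* catches her only if her test is positive or she plans a pregnancy. A woman who will stop contraception without planning to conceive meets neither.
- *The investigator qualifier* at the end of item 7 lets the investigator judge the facts. It does not alter the connective.
- *Section 9.10, pregnancy* applies only after pregnancy has occurred, and withdrawal there is discretionary.
- *Section 9.10, meeting an exclusion criterion* applies item 7 as worded, so it carries the same gap forward.
- *Section 8.3 and Table 3* state no separate contraception requirement.

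**Comparison with the protocol's own drafting.** Where other exclusions pair a present or past state with a future intention, either is enough: exclusion 6 (positive test, or planned pregnancy), exclusion 11 (past, or planned, glucocorticoids), and exclusions 18 and 19 (recent and planned transfusion or erythropoietin as separate items). Inclusion 12 properly uses *and* for its insulin condition, because it is a positive requirement with both parts needed. Item 7 reads like a requirement of that kind turned into a negative without the connective being changed.

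**The case against.** The strongest reply is that the practical reach is small. Exclusion 6 already removes women who stop contraception in order to conceive. What remains is women who would stop without planning a pregnancy, over two to three months. The investigator makes the determination, and many would apply the evident sense of item 7. All of this stands, and it limits the importance of the point. It does not cure the wording.

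A reader might infer three stronger things that the documents do not support.

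- *That item 7 wrongly lets in a woman who is not using contraception but agrees to do so.* The word *continue* makes it doubtful that she escapes item 7 at all. Nor do the documents show whether the sponsor meant to exclude a woman willing to start. Inclusion 13 accepts willingness to learn carbohydrate counting in place of present ability, so accepting willingness would not be foreign to this protocol. For the same reason, simply replacing *and* with *or* would settle a question that the documents leave open.
- *That the gap causes avoidable loss from the primary analysis.* The ITT population is everyone who starts the study period (Protocol 14.5, SAP 7.1.3), and Section 9.10 keeps data up to exit for analysis. A subject withdrawn for pregnancy after Visit 4 stays in ITT with whatever study-period data she has. She would leave the SAP's per-protocol set, which requires completion, and would not count toward the 50 completers. Only withdrawal during run-in keeps a subject out of ITT, and enrolment of up to 75 allows for dropouts.
- *That a specific device hazard in pregnancy is shown.* The risk tables in Section 10.1 list no pregnancy-specific risk. Exclusions 6 and 7 and the withdrawal entry show that the protocol intends to avoid pregnancy during the study; they do not describe or quantify a harm.

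**Conclusion.** The point holds in one firm case: a sexually active woman able to conceive, using contraception at Screening and unwilling to commit to it for the study, is not excluded by item 7. No other entry criterion catches her unless her test is positive or she plans pregnancy. Not excluded by item 7 does not mean eligible, since all other criteria still apply.

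This is a minor eligibility-drafting error whose rationale is participant safety. It has no effect on the sample size, power, alpha or the primary test. How many women it might affect cannot be derived, because the documents give no figures on sex, contraceptive use or willingness to continue. The conclusion rests on reading the connective as written and on the reference to the study's duration showing that a lasting commitment was intended.

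**What to change.** Reword item 7 identically in Section 8.4 and in the synopsis so that, for a sexually active woman able to conceive, not agreeing to use effective contraception for the duration of the study is sufficient on its own to exclude. The sponsor should also state explicitly whether a woman who is not using contraception at Screening but agrees to start is eligible; the documents do not settle this and the review should not presume it.

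The edit is one sentence in two places, with no change to any analysis. It is not entirely free: under Section 16.8 an amendment goes to the ethics committee for approval or notification and is signed by investigators. It could be carried with the next amendment, with a clarification to sites in the meantime.
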